## 9.3 Data collection

This study will use Electronic Data Capture (EDC) and the designated investigator staff will enter the data required by the protocol into the eCRF. The eCRFs have been built using fully validated secure web-enabled software that conforms to 21 CFR Part 11 requirements, Investigator site staff will not be given access to the EDC system until they have been trained. Automatic validation programs check for data discrepancies in the eCRFs and, allow modification or verification of the entered data by the investigator staff.

The Principal Investigator is responsible for assuring that the data entered into eCRF is complete, accurate, and that entry and updates are performed in a timely manner.

Mutational analysis data will be generated by CLIA certified local labs. We anticipate that the data available in the report will vary from lab to lab. The PI will enter data directly onto the eCRF to verify that the patient meets the requirements of "pathway activation" as outlined in the inclusion criteria [Section 5](#). Anonymized lab reports will be collected to gather information regarding pathway activations.

Laboratory assessments for hematology, biochemistry, coagulation, urinalysis, MUGA and ECGs will be collected locally and entered directly onto the eCRFs.

## 9.4 Database management and quality control

This study will be using eCRFs and the designated CRO will review the data entered by investigational staff for completeness and accuracy. Electronic data queries stating the nature of the problem and requesting clarification will be created for discrepancies and missing

values and sent to the investigational site via the EDC system. Designated investigator site staff are required to respond promptly to queries and to make any necessary changes to the data.

Concomitant treatments and prior medications entered into the database will be coded using the WHO Drug Reference List, which employs the Anatomical Therapeutic Chemical classification system. Medical history/current medical conditions and adverse events will be coded using the Medical dictionary for regulatory activities (MedDRA current version) terminology.

Data from the screening molecular analysis will be collected locally and entered directly onto the eCRF. Tissue samples for pathway activation confirmation will be analyzed centrally.

At the conclusion of the study, the occurrence of any protocol violations will be determined. After this action has been completed and the data has been verified to be complete and accurate, the database will be declared locked and the data made available for data analysis. Authorization is required prior to making any database changes to locked data, by joint written agreement between the US Oncology Medical Affairs Franchise Head and the US Oncology Medical Affairs Franchise Vice President.

After database lock, the investigator will receive a CD-ROM or paper copies of the patient data for archiving at the investigational site.

## **10 Statistical methods and data analysis**

All data except the primary efficacy variable clinical benefit rate will be analyzed by a designated CRO in collaboration with Novartis. Any data analysis carried out independently by the investigator should be submitted to Novartis before publication or presentation. The data from all centers that participate in this study will be combined in the final safety and efficacy analysis.

### **10.1 Analysis sets**

#### **10.1.1 Full Analysis Set**

The Full Analysis Set (FAS) will include all patients who have received at least one dose of study drug.

FAS will be used for the analysis of efficacy endpoints.

#### **10.1.2 Safety Set**

The Safety Set will include all patients who received at least one dose of study treatment and had at least one post-baseline safety assessment.

Please note: the statement that a patient had no adverse event (on the Adverse Event eCRF) constitutes a safety assessment.

## **10.2 Patient demographics/other baseline characteristics**

Demographic and other baseline data (including disease characteristics) will be listed and summarized by patients groups formed by the type of cancer at study entry using the FAS. Additional groups may be added based on enrollment (See [Appendix R](#)). Categorical data, such as gender, race, etc., will be presented by frequencies and percentages. Descriptive summary statistics (e.g., frequency, mean, median, range and standard deviation) will be used to present numeric data.

## **10.3 Treatments (study treatment, concomitant therapies, compliance)**

### **10.3.1 Study medication**

Duration of study treatment exposure, cumulative dose and dose intensity will be summarized by the patient groups as above using the Safety Set. The number of patients with dose changes/interruptions will be presented along with reasons for the dose change/interruption. The safety set will be used for the tables and listings.

### **10.3.2 Concomitant therapies**

Concomitant medications and significant non-drug therapies taken concurrently with the study drugs will be listed and summarized for the FAS by Anatomical Therapeutic Chemical Classification System (ATC) term, preferred term and treatment arm by means of frequency counts and percentages. These summaries will include medications starting on or after the start of study treatment (defined as cycle 1 day 1) or medications starting prior to the start of study treatment and continuing after the start of study treatment.

Any prior concomitant medications or significant non-drug therapies starting and ending prior to the start of study treatment will be listed. The safety set will be used for all above mentioned concomitant medication tables and listings.

## **10.4 Primary objective**

The primary objective is to assess clinical benefit associated with ribociclib treatment based on local investigator assessment.

For patients with solid tumors the assessment criteria will be RECIST 1.1 and will include responses of CR or PR or SD  $\geq$  16 weeks. For hematologic tumors other appropriate hematological response criteria will apply and are included in the appendices.

For solid tumors, an assessment of CR or PR using RECIST 1.1 must be confirmed at least 4 weeks after initial observation. If the two assessments differ, the best overall response will be determined by [Table 3-3](#) of [Appendix B](#).

### **10.4.1 Variable**

The primary efficacy variable is the clinical benefit rate (CBR) (e.g. defined as CR or PR or SD  $\geq$  16 weeks for solid tumors).

#### 10.4.2 Statistical hypothesis, model, and method of analysis

The study will enroll patients from at least 8 tumor cohorts, with each tumor cohort containing possible tumors of interest as shown in [Appendix R](#).

We let  $Y_i$  be the response indicator for the  $i^{\text{th}}$  subject, and let  $R_g$  be the assumed probability of response within a control population and  $\pi_g = \Pr(Y_i = 1 \mid g_i = g)$  be the underlying probability of response for group  $g$  within the trial. We transform to the logit scale for modeling purposes. Let  $\theta_g$  be the mean log odds treatment effect, i.e.:

$$\theta_g = \log\left(\frac{\pi_g}{1 - \pi_g}\right) - \log\left(\frac{R_g}{1 - R_g}\right)$$

Thus,  $\theta_g$  is the group specific logistic regression coefficient for group  $g$ . The primary analysis is a set of group specific tests that  $\theta_g > 0$ , meaning that the treatment is better than the assumed control rate for that group. Thus, we wish to test the set of hypotheses

$$H_{0g} : \theta_g \leq 0$$

$$H_{1g} : \theta_g > 0$$

We proceed in a Bayesian fashion, assigning a prior distribution (discussed below) and computing the posterior probability of  $H_{1g}$  within each group  $g$ . If, at the final analysis,

$$\Pr(\theta_g > 0 \mid \text{data}) > 0.80$$

Then group  $g$  will be declared a success (thus, the final analysis produces a separate decision for each group). The trial also allows for early stopping of groups..

The statistical design borrows information across groups with a hierarchical model. The hierarchical model allows dynamic borrowing of information between groups such that more borrowing occurs when the groups are consistent and less borrowing occurs when the groups differ. In this way, the model is a compromise between the two alternate extremes of either a completely pooled analysis or a separate analysis in each group. We additionally incorporate a clustering mechanism that allows borrowing within clusters but treats clusters separately. This minimizes borrowing across groups that are quite different in terms of CBR.

The hierarchical approach involves two stages. The goal of both stages is to allow the data to drive the amount of borrowing across groups. If the data indicate a large amount of borrowing is appropriate (due to similar results), the model will borrow more and thus increase the overall power of the trial within each group. In contrast, if the data indicate a small amount of borrowing is appropriate (due to dissimilar results) the model will adjust and each group will stand more on its own. This “dynamic” borrowing property is distinct from other approaches which use a fixed informative prior or apriori assume an amount of borrowing across groups.

The first stage of model places the groups into distinct clusters. The purpose of this stage is to minimize borrowing of information across groups that appear to be quite different. Thus, for example, should 2 of the groups appear similar while the others differ significantly, the model may place a large probability on two clusters, one containing the two similar groups with the other containing the remaining groups. The model incorporates the uncertainty of the data in this determination, producing a probability distribution over the possible clusterings. Thus, in

our example, the model may consider it highly likely that the 2 similar groups are in one cluster with the remaining groups in another, but it would also retain lower probabilities on the possibility all groups are in one cluster (e.g. we are simply seeing differences in the two groups by chance) as well as other possibilities. The complete analysis averages over this uncertainty. This clustering approach is implemented through a Dirichlet Process Mixture (DPM) model, described in the appendix.

At the second stage, we place hierarchical models over the groups within each cluster (thus, conditional on the clustering, there is no borrowing of information across clusters, only within clusters). The hierarchical model assumes that the  $\theta_g$  have an across groups distribution

$$\theta_g \sim N(\mu, \tau^2)$$

The across group mean  $\mu$  and variance  $\tau^2$  are unknown, and hence have a prior distribution which is combined with the data to produce estimates of  $\mu$  and  $\tau^2$ .

The variance component  $\tau$  controls the degree of borrowing among groups. Small values of  $\tau$  result in a greater degree of borrowing while large values of  $\tau$  correspond to less borrowing. The parameter  $\tau$  is estimated using the data, so the observed between group variation is a key component of the model behavior.

Combined, the two stages allow groups with similar results to borrow information between them (they will have a high probability of being in the same cluster) while groups with different results with borrow far less information between them (they will have a low probability of being in the same cluster).

Details of the hierarchical model is provided in [Appendix R](#).

#### **10.4.3 Evaluation of trial success and futility**

The clinical benefit rate will be evaluated for futility and early success by comparing posterior quantities for the rate to pre-specified early stopping criteria. The evaluation are planned to occur after the first 30 patients overall (across all groups) have been dosed for at least 16 weeks or discontinued, and then every 13 weeks thereafter until the end of the study. An additional CBR evaluation will be performed at the end of the study.

##### **Early Futility**

If there is less than 10% probability that the response rate in a subgroup exceeds the historical rate  $R_g$ , then the group will stop enrollment early for futility. Formally, enrollment will stop early for futility if:

$$\Pr(\pi_g > R_g) < 0.10.$$

A group is only eligible for early stopping once a minimum of 10 patients have been evaluated for response in that group.

##### **Early Success**

If there is at least 95% probability that the response rate in a subgroup exceeds the historical rate, then the subgroup will stop enrollment early for success. Formally, enrollment will stop early for success if:

$$\Pr(\pi_g > R_g) > 0.95.$$

A minimum of 15 subjects will need to be evaluated prior to declaring a group to be efficacious.

## Final Analysis

The final analysis will occur when both accrual and follow-up are complete for all groups. If, at the completion of the trial, there is at least 80% probability that the response rate in a group exceeds the historical rate, then the group will be considered a success. Formally:

$$\Pr(\pi_g > R_g) > 0.80.$$

### 10.4.4 Handling of missing values/censoring/discontinuations

A patient who has not progressed or died at the date of the analysis cut-off would have his/her PFS and OS censored at the time of the last adequate assessment before the cut-off date. Any disease assessment indicating response status other than “unknown” or “not done” is considered an adequate response assessment.

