### 10.5.2 Other secondary efficacy objectives

The secondary objectives of the study:

- To assess progression free survival (PFS) based on local investigator assessment per RECIST 1.1 or other appropriate hematological response criteria
- To assess overall survival
- To assess duration of response (DOR) based on local investigator assessment per RECIST 1.1 or other appropriate hematological response criteria
- To assess safety and tolerability

The secondary efficacy variable progression free survival (PFS) is defined as the time from the date of first dose to the date of first documented disease progression or relapse or death due to any cause.

PFS will be summarized and graphed using the Kaplan-Meier product-limit method for each patient group. Patients who drop-out without progression will be censored at the time of last adequate assessment. The estimates of the 25th, median, 75th percentiles of the PFS and their 95% confidence intervals will be provided, if applicable.

Overall survival (OS) is defined as the time from the date of first dose to the date of death due to any cause. If a patient is not known to have died, survival time will be censored at the date of the last contact.

OS will be summarized and graphed using the product-limit method as above.

The duration of response applies only to patients whose best response was PR or CR. For patients with solid tumors the assessment criteria will be RECIST 1.1 and will include responses of CR and/or PR. For hematologic tumors other appropriate hematological response criteria will apply and are included in the appendices. The duration of response is defined as the time from the first documented response to the date first documented disease progression or relapse or death due to any cause. The duration of response will be summarized descriptively for each patient group.

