8.5	Modeling Details	30
9	References	32

1 Introduction

The primary efficacy variable, clinical benefit rate, will be analyzed by a Novartis designated Contract Research Organization (CRO), [REDACTED]. Analysis details are provided in Appendix R of the protocol, which is also included in Section 8 of this Report Analysis Plan (RAP).

[REDACTED]
[REDACTED]
All other data will be analyzed by a different Novartis-designed CRO, [REDACTED] according to Section 10 of the study protocol which will be available in Appendix 16.1.1 of the Clinical Study Report (CSR). Important information is given in the following sections and details will be provided, as applicable, in Appendix 16.1.9 of the CSR. All statistical analyses will be performed using SAS® Version 9.3 (or higher).

2 Statistical and analytical plans

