4.5 Overall Survival (OS)

Overall survival, defined as the time from the date of the first dose of ribociclib to the date of death due to any cause will be analyzed using methods similar to those stated above for PFS. That is, the 25th percentile, median, and 75th percentile of survival time with corresponding 95% CIs will be provided; survival curve and survival rates at time points, such as 3, 6, 9, 12, 18, and 24 months will also be presented. Patients who are alive at the time of discontinuation/completion of the study will be censored at the last contact date (as defined in Section 2.5.7). Analyses will be based on all tumor types combined. For tumor types that have ten (10) or more patients, separate summaries will be performed by the tumor type.

Handling missing month/day in date of death

For rare cases when either day is missing or both month and day are missing for the date of death, the follow imputation rules will be implemented:

- If only day is missing, then impute maximum of [(1 mmm-yyyy), minimum of (any valid date from data base used for deriving last contact date + 1, cut-off date)].
- If both day and month are missing, then impute maximum of [(1 Jan-yyyy, minimum of (any valid date from data base used for deriving last contact date + 1, cut-off date)].

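### Protocol 10.4.4 censors overall survival at the last disease assessment for patients alive without progression, which contradicts the last-contact rule in Protocol 10.5.2 and the SAP

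*Protocol*

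**What the plan says.** Protocol 10.4.4 sets one censoring date for two endpoints. A patient who, at the analysis cut-off, has neither progressed nor died "would have his/her PFS and OS censored at the time of the last adequate assessment before the cut-off date". The sentence after it explains adequacy in terms of response status, beginning "Any disease assessment indicating response status other than".

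Protocol 10.5.2, where OS is defined, has a different rule: "If a patient is not known to have died, survival time will be censored at the date of the last contact".

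The SAP agrees with 10.5.2. SAP 4.5 states: "Patients who are alive at the time of discontinuation/completion of the study will be censored at the last contact date". SAP 2.5.7 derives that date for anyone not known to be dead at the cut-off from visit assessments, medication dates, adverse event dates and the survival form, and it names OS censoring as the use of the date. In the SAP, the last adequate tumor assessment is a censoring date only for duration of response (4.3) and PFS (4.4).

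Two further places bear on which rule governs. SAP 1 says the non-primary data are analysed "according to Section 10 of the study protocol", and that section contains both rules. SAP 2.3, which lists departures from the protocol, does not mention OS censoring.

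**The concern.** The last disease assessment is the right censoring date for PFS, because progression is unknown after it. It is the wrong date for OS, because survival status is still being collected.

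The two dates can be far apart. Scans fall at weeks 8 and 16, then every 16 weeks, and stop at progression or end of treatment (Protocol 4.1.1). Protocol 7.1.4.2 plans no efficacy follow-up. Clinic visits continue each 28-day cycle, and survival contact continues every 3 months after treatment (7.1.4.3). A progression-free patient at week 30 was last scanned at week 16 but seen at day 1 of cycle 8, which is 7 × 4 = week 28. Rule 10.4.4 discards those 12 weeks.

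Censoring then depends on outcome: the patient who lives loses follow-up time, and the patient who dies does not. OS is a stated secondary endpoint, with medians and landmark rates planned in SAP 4.5.

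The effect is largest at the CSR cut-off, set when the last patient on treatment completes four cycles (SAP 2.2). That analysis could become the main OS report, because the sponsor may stop survival follow-up if the primary endpoint is not met (Protocol 4.1.2 and 7.1.4.3).

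**Working it through.** **Direction.** The Kaplan-Meier estimate is S(t) = ∏(1 − dᵢ/nᵢ) over death times up to t. The last contact date includes all assessment dates, so it is never earlier than the last scan. Moving a living patient's censoring date back to the last scan leaves every dᵢ unchanged and can only reduce nᵢ. Each factor is then equal or smaller, so the OS curve can only fall.

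**Size.** The documents state no OS median, event count or power, so there is no figure to reproduce. A simulation compared the censoring rules on the same data, with 200,000 patients per scenario to remove sampling noise.

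Inputs from the documents:
- Accrual over about 9 months: August 2014 to 8 May 2015 (Protocol, Amendment 3).
- Scan and survival-contact schedules as described above, with the end-of-treatment scan rule of Table 7-1.
- Cut-offs at 16 weeks after last enrolment (CSR) and at 2 years after last enrolment.
- Stopping without progression: in the first-in-human study, 8 + 3 + 1 = 12 patients stopped for adverse events, withdrawn consent or loss to follow-up, against 96 for progression (Protocol 1.2.1.2.1). The ratio is 12/96 = 0.125, and 0.05 and 0.20 were used to bracket it.

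Assumptions not in the documents:
- Exponential times, with hazard = ln 2 / median.
- Median time to progression of 2 or 4 months.
- Median survival after progression or discontinuation of 4 or 8 months.
- Hazard of death before progression equal to 0.1 of the progression hazard.

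Results at the CSR cut-off, as median OS in months / 6-month OS:

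| Time to progression | Survival afterwards | Stopping ratio | Last contact | 10.4.4 as worded | Last scan for all living |
|---|---|---|---|---|---|
| 2 | 4 | 0.05 | 5.9 / 0.49 | 5.7 / 0.47 | 4.9 / 0.37 |
| 2 | 4 | 0.20 | 5.7 / 0.47 | 5.4 / 0.44 | 4.7 / 0.34 |
| 2 | 8 | 0.05 | 8.7 / 0.66 | 8.3 / 0.64 | 5.9 / 0.49 |
| 2 | 8 | 0.20 | 8.5 / 0.65 | 7.8 / 0.61 | 5.6 / 0.46 |
| 4 | 4 | 0.05 | 8.0 / 0.65 | 7.6 / 0.62 | 6.8 / 0.57 |
| 4 | 4 | 0.20 | 7.7 / 0.62 | 7.1 / 0.58 | 6.4 / 0.53 |
| 4 | 8 | 0.05 | 10.7 / 0.76 | 9.9 / 0.74 | 7.9 / 0.67 |
| 4 | 8 | 0.20 | 10.4 / 0.75 | 9.3 / 0.72 | 7.7 / 0.65 |

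For 10.4.4 as worded, the loss in the median runs from 5.9 − 5.7 = 0.2 months (0.2/5.9, about 3%) to 10.4 − 9.3 = 1.1 months (1.1/10.4, about 11%). The loss in 6-month OS is 2 to 4 points. The rule affects the 12% to 33% of patients who are alive without documented progression, whose median gap from last scan to last contact is 4 to 12 weeks.

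At 2 years after last enrolment the loss in the median under 10.4.4 as worded is 0 to 0.1 months, because few such patients remain (at most 2%).

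Two cautions apply. The comparison is with the last-contact rule, not with the truth: at the CSR cut-off that rule also falls short of the true median (5.7 to 10.7 against 5.9 to 12.4 months), because deaths count up to the cut-off and living patients only to their last contact. The 12-month rate differs by more (2 to 10 points), but little weight should go on it. Hardly anyone has 12 months of follow-up by then, and in the first scenario the last-contact estimate is itself 0.07 against a true 0.20.

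**The case against.** The strongest reply is that the working rule is already clear. SAP 2.5.7 and 4.5 name last contact for OS, and nothing in the SAP censors OS at a scan. SAP 1 refers to protocol Section 10 but goes on to say that the important information is in its own sections. Within Section 10, OS is defined in 10.5.2, whereas 10.4.4 sits under the primary objective. A programmer would most likely use last contact. This stands, and it keeps the severity low. It does not remove the contradiction, because nothing records that 10.4.4 is superseded.

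A second reply is that the definition in 10.4.4 is of an adequate *response* assessment, and that 7.1.4.3 speaks of survival assessments, so *assessment* might be read more widely for OS. That is possible. But 10.4.4 gives one date for both endpoints and explains adequacy only through disease assessment, so the scan date is the likelier meaning.

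A third is that OS is descriptive: SAP 2.2 plans no testing outside the primary variable, SAP 7 gives secondary objectives no power consideration, and no stopping or success rule uses OS. This also stands.

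A reader might infer something stronger: that 10.4.4 censors every living patient at the last scan and so biases OS sharply. On that reading the median falls by 1.0 to 2.9 months and 6-month OS by 8 to 19 points at the CSR cut-off, and the median by 0 to 0.8 months at two years. The documents do not support it. The sentence is limited to patients with neither progression nor death. A living patient who has progressed falls outside it and is reached only by the last-contact rule. The broad reading requires splitting the condition (not progressed for PFS, not died for OS). That the wording can be stretched this way is a further reason to correct it.

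**Conclusion.** The contradiction is real and lies in current text. For patients alive without progression, 10.4.4 gives an OS censoring date that conflicts with 10.5.2 and with the SAP, and following it can only lower the OS curve.

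The size is small to moderate at the CSR cut-off (about 0.2 to 1.1 months on the median and 2 to 4 points on 6-month OS) and negligible at full follow-up (0 to 0.1 months). The direction follows from the estimator. The sizes rest on the assumed progression and survival times.

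This is a low-severity correction. No decision in the trial depends on OS, and an analyst who follows the SAP will already use the right date. The documents do not support a claim that the planned OS analysis is invalid or sharply biased.

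**What to change.** Preferred: in Protocol 10.4.4 delete *and OS*, so that the last-adequate-assessment rule governs PFS only, and add a reference to 10.5.2 and SAP 2.5.7 for OS. The edit is trivial, but Protocol 12.1 requires a written amendment with sponsor and ethics approval, so it is best carried with another amendment.

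Cheaper alternative: add one line to SAP 2.3 stating that OS is censored at the last contact date of SAP 2.5.7, in place of Protocol 10.4.4. This needs no amendment.

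Neither route needs new data. Neither needs reprogramming if SAP 4.5 is already being followed.
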